CVD and CVD Risk Factors among Persons with SMI. CVD is the leading cause of preventable death among persons with SMI. Diet and physical activity habits are typically poor in this population which contribute, along with metabolic side effects of many psychotropic medications, to high rates of obesity, other CVD risk factors, and CVD. Behavioral interventions promoting healthy diet, exercise, and weight loss are critically needed, but must be adapted to challenges particularly to the SMI population including memory impairment, limited executive function, and residual psychiatric symptoms.

The ACHIEVE Trial. The NIMH-funded ACHIEVE trial was the first to demonstrate that an adapted behavioral intervention leads to clinically significant weight loss at 18 months among persons with SMI (mean 7 lbs. weight loss, net 3% loss). The magnitude of weight loss among individuals with SMI participating in ACHIEVE was similar to the magnitude observed in efficacious weight-loss trials in general populations. The ACHIEVE intervention combined group

and individual weight-management sessions with group exercise sessions delivered in community mental health programs. The curriculum focused on repeated delivery of six key messages: avoid sugary drinks, avoid junk food, eat 5 servings of fruits/vegetables per day, portion control, smart snack habits, and regular physical activity. The ACHIEVE curriculum was predominantly delivered by trained study interventionists, though mental health program staff delivered some video-assisted group exercise sessions. In light of the obesity epidemic in persons with SMI, there is an urgent need to scale-up interventions like ACHIEVE.

Considerations for Scaling up ACHIEVE. To realize the full public health potential of ACHIEVE, the curriculum needs to be modified for delivery by community mental health center staff. Adaptations should ease implementation, but maintain fidelity to the core content of ACHIEVE (Table 1).

Table 1. ACHIEVE vs. ACHIEVE-D Comparison	
ACHIEVE Trial	Proposed ACHIEVE-D Dissemination
Type and Frequency of Contact	

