Recruitment. We will recruit participants from Prologue, which is a PRP based in Baltimore with whom the study team has a long-term relationship (see letter of support). We will use similar methods as in prior and ongoing studies. We will recruit consumers with SMI who are willing to participate and have no contraindications to participating in a diet and physical activity program (see eligibility criteria described in following section).

We will make presentations during regular consumer meetings at the PRP where we will provide information about the study. We will also display recruitment flyers in the PRP (Flyer). We will use a telephone script to handle all calls or in-person inquiries generated from these presentations and flyers (Screening Script). Consumers who are interested in participating will sign up to attend a consent/screening visit. To address privacy issues during recruitment, all participants who are contacted or who approach us for recruitment will be assured that the research staff at Johns Hopkins will be the only ones to see their information, and that the information we collected will be kept private and be used only for the research study we are discussing. If the potential participant chooses not to enroll in the study or does not qualify to be in the study, then his/her information will be destroyed.

Consent & Screening. We plan to screen a total of 20 consumers with the goal of enrolling approximately 10 into the study. Participant eligibility will be determined at the consent/screening interview (Table 3).

Consent

The study will be explained in detail to the potential participants in a one-on-one format onsite at the PRP in a private room. Informed consent for the study will be obtained from each eligible participant at the beginning of this visit (Consumer Written Consent). In particular, consumers will be advised of the voluntary and confidential nature of participation. Consumers will be asked questions about the study procedures to test their understanding. They will also be provided the contact information of the principal investigator. We will emphasize that their participation in the study will not affect their care at the PRP or Johns Hopkins. After consent is obtained, then potential participants will be screened.

Screening

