Procedures. This data will be collected during study visits at baseline and follow-up for enrolled participants held onsite at the PRP in a private room. Surveys will be administered in-person by trained research assistants. All data will be collected on Johns Hopkins encrypted, password protected laptop computers and entered into a RedCap database. Because of consumers' generally low literacy and problems with cognition, all instruments will be interviewer administered to decrease the burden on participants and improve validity of data collection. Enrolled participants will complete baseline data collection measures (Table 3).

During the intervention, we will also collect data on participants regarding attendance, weight from weigh-ins during the sessions, hours per week each consumer participated in ACHIEVE-D exercise classes, as well as diet and physical activity via weekly self-reported logs.

We will video record each class session (3 classes per week for 8 weeks – 24 sessions total) and grade the sessions using a fidelity tool (ACHIEVE-D Fidelity Tool), which measures to what extent the coach implements the core components of ACHIEVE-D and uses a motivational interviewing delivery style. Once videos are evaluated for fidelity, any that are not needed will be destroyed; some will be stored on a Johns Hopkins secure network drive and used for future training in fidelity monitoring. In addition, short video clips from these sessions may be incorporated into materials for the larger R34 study including to train coaches.

After completion of the intervention, consumers will complete a survey including asking questions regarding satisfaction with the curriculum, self-reported sugar sweetened beverages and sedentary behaviors, and anthropometric measurements will be repeated at this time. We will also repeat other measures as described in Table 3.

Table 3. Data Collection Schedule

	Consent/ Screening	Baseline	Follow-up	
			During	Post
Informed consent	x			
Demographics	x			
Medical history	x			x
Medications	x			
Substance use (ASI-Lite)	x			
Exercise pre-participation screening (2018 PAR-Q+)	x			
Weight	x	x	x	x
Height	x			x
Primary Outcomes				
Consumer focus group				x
PRP staff & peer leader focus group				x
Secondary Outcomes				
Diet				
EARLY Eating Away from Home Q		x		x
EARLY SSB Consumption Q		x		x
Physical Activity				
CARDIA/EARLY Q – sedentary behavior		x		x
Eating Behaviors				
Palatable Eating Motives Scale (PEMS) – Coping Subscale		x		x

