Trait Food Craving Q – Reduced Form		x		x
Reward-based Eating Drive (RED) Scale		x		x
Psychological & Support				
Perceived Stress Scale (PSS)		x		x
Important Others' Q		x		x
Anthropometric Measurements				
Waist circumference		x		x
Process Measures				
Consumer attendance & exercise at group sessions			x	
Consumer food and physical activity logs			x	
Consumer Satisfaction Q - Nabati				x
Coach Fidelity to ACHIEVE-D			x	

Abbreviations: SSB – sugar-sweetened beverage; Q – questionnaire

Below we describe the planned secondary outcomes:

Acceptability

A 12-item Consumer Satisfaction Questionnaire based on the instrument developed by Nabati and colleagues will be used to determine acceptability. Following the intervention, in addition to the focus group, we will use this standard measure of satisfaction with the intervention. We will also examine participation as a reflection of acceptability. Participation in intervention sessions will be measured by attendance at the group classes, the number of sessions attended, and proportion attending at least 80% of sessions.

Date: May 15, 2019

Principal Investigator: [name]

Application Number: IRB00194122

Diet

We will administer the EARLY Sugar-Sweetened Beverage (SSB) questionnaire at baseline and post-intervention, which has been selected by the NIH as Accumulating Data to Optimally Predict Obesity Treatment (ADOPT) Core Measures for diet.

Physical Activity

We will administer the sedentary behavior inventory from CARDIA/EARLY at baseline and post-intervention, which has been selected by the NIH as ADOPT Core Measures for self-reported physical activity.

Weight & Waist Circumference

Weight will be measured at baseline and post-intervention using standard procedures as described in the screening section above. Waist circumference is measured using a tape, according to a standardized protocol at baseline and post-intervention.

Below we describe the other planned survey measures in this study:

Demographics

Most demographic data will be obtained from Prologue's intake assessment, but we will obtain updated marital status and living arrangements as well as confirm educational level. This data will be collected at the screening visit.

Medical History

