We will measure medical conditions with a short checklist of conditions. Each consumer is required to have a physical exam annually, and a list of medical conditions is kept in the Prologue chart. Potential participants will consent to allow us to review their medical records at Prologue. We will assess conditions by reviewing the medical chart and by interview. Any discrepancies will be confirmed by participants' primary care physicians. This data will be collected during screening.

Medications

Prologue tracks all medications and medication changes. We will measure medications including dose, route and frequency at baseline by compiling a list of medications from the medical chart. Potential participants will be asked to confirm this list with input from caregivers, as needed. Medication information will be updated at the end of the pilot intervention.

Diet and Eating Habits

We will administer the EARLY Eating Away from Home questionnaire and 3 questionnaires regarding eating habits as listed in Table 3, which have been selected by the NIH as ADOPT Core Measures for these domains.

Psychological & Support

We will administer 2 questionnaires regarding psychological and social support domains as listed in Table 3, which have been selected by the NIH as ADOPT Core Measures for this area.

Procedures related to Hypothesis 2 – PRP staff and peer leaders

Date: May 15, 2019

Principal Investigator: [name]

Application Number: IRB00194122

We will recruit staff and peer leaders from Prologue, who will be invited to observe all the sessions during this pilot. We aim to recruit at least 4 PRP staff members and at least 1 peer leader to observe however, we have the capacity for up to 20 staff or peers.

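### Do the missing end-of-study medication mark in Table 3, the two labels for six questionnaires, and Section 7b's silence on weight and waist call for a change?

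*Combined protocol and SAP*

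**What the plan says.** **Medications.** Section 4 (Medications) has a list compiled from the chart at baseline and confirmed by the participant, and then states: "Medication information will be updated at the end of the pilot intervention". It also notes that "Prologue tracks all medications and medication changes". Table 3 marks the Medications row once, under Consent/Screening. On post-intervention collection in general, Section 4 says "We will also repeat other measures as described in Table 3".

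**Outcome labels.** The text of Section 4 has two lists. The first opens with "Below we describe the planned secondary outcomes" and covers acceptability (satisfaction and attendance), the sugar-sweetened beverage (SSB) questionnaire, the sedentary behavior inventory, and weight and waist. The second opens with "Below we describe the other planned survey measures in this study" and includes Eating Away from Home, three eating-habit questionnaires, and two on psychological and support domains. Table 3 has a secondary heading but no heading for other measures, and all six of these questionnaires come after the secondary heading.

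**Weight and waist.** The first list says "Weight will be measured at baseline and post-intervention using standard procedures as described in the screening section above" and gives waist the same two time points. Section 7b names t-tests and chi-square tests for diet and physical activity changes, with the Wilcoxon signed-rank test as the substitute for non-normal data. It mentions neither weight nor waist. Section 4a states a general intention to compare consumers' outcomes before and after, and Section 7c adds no method.

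**The concern.** Staff who work from the schedule rather than the text could skip the medication update, because the text itself points to Table 3 for what is repeated. The protocol gives a reason to care: Section 3 lists "metabolic side effects of many psychotropic medications" among the contributors to obesity. The design has no control group and is small ("We plan to screen a total of 20 consumers with the goal of enrolling approximately 10 into the study"). One or two medication changes would touch 10% to 20% of 10 participants and could colour the weight result.

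The label conflict looks like room to choose. If the status of six questionnaires is unsettled, the pre-post results reported as secondary could be picked after the data are seen. And in a study of a weight-loss curriculum, a statistics section that names no analysis for weight change is a visible hole.

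**Working it through.** No power or error-rate figure is involved, so the check is a row-by-row comparison and a count.

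**Step 1: Table 3 against the text, rows with a post-intervention mismatch**

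| Row | Marks in Table 3 | Text of Section 4 | Result |
|---|---|---|---|
| Medical history | Consent/Screening, Post | Collected at screening | Post mark not in text |
| Medications | Consent/Screening | Baseline list, then an end-of-intervention update | Post mark missing |
| Height | Consent/Screening, Post | Measured a single time, at baseline | Post mark not in text |

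Three rows disagree with the text, not one. The first two are adjacent and disagree in opposite directions. Moving the Post mark from Medical history down one row reconciles both. The shift may lie in the source table or in its conversion from PDF, and the original table would settle which. Height remains as a separate small mismatch.

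**Step 2: questionnaires with conflicting status**

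- Under Table 3's secondary heading, marked at Baseline and Post: Eating Away from Home, SSB, sedentary behavior, Palatable Eating Motives (coping), Trait Food Craving, Reward-based Eating Drive, Perceived Stress, Important Others. Total 8.
- Secondary in the text: SSB and sedentary behavior. Total 2.
- In the text's list of other measures: 1 + 3 + 2 = 6, which agrees with 8 − 2 = 6.

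**Step 3: number of pre-post secondary measures**

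- By the text: 2 questionnaires + weight + waist = 4.
- By Table 3 alone: 8 questionnaires + waist = 9. Weight stands above the outcome headings in Table 3, so it is not in that block.
- By Table 3 with weight added from the text: 9 + 1 = 10.

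These counts take Table 3's secondary heading to run over all the domains below it. If it covered only Diet and Physical Activity, just one questionnaire (Eating Away from Home) would conflict. The wider reading is the likelier one, because waist and the satisfaction questionnaire, both secondary in the text, also come later in the table.

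**Step 4: methods in Section 7b**

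Of the text's 4 pre-post secondary measures, 2 (SSB and sedentary behavior) have a named method and 2 (weight and waist) do not. Section 7b does not use the word paired. But its substitute for the t-test is the signed-rank test, which works on within-person differences, so the t-test it replaces must be the paired one. Weight and waist are continuous and measured on the same people at the same two visits. The same pair of methods applies to them without any new decision.

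**Step 5: what depends on these points**

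Both hypotheses in Section 2 concern acceptability and feasibility. Section 7a analyses the primary outcomes by coding focus-group transcripts. No significance level, power or decision rule is attached to weight, waist or any questionnaire.

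**The case for a change.** The strongest case for acting is that the remedy is nearly free: one table mark, one agreed list and one sentence in Section 7b, with no added visits or burden. Section 8a itself foresees that diet change and exercise may require some medication doses to be adjusted, so the update is not idle. The label conflict also reaches into the analysis: 7b covers diet outcomes, and Table 3 files Eating Away from Home under Diet while the text's secondary diet measure is SSB alone, so its place in 7b is unclear.

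What stands is that the mismatches are real and that Table 3 and the text should read alike. What does not stand is the harm. An empty cell does not cancel an explicit sentence, and for about 10 people any missed update can be recovered from a chart that records medication changes. Whether a questionnaire is called secondary or other changes neither its collection (all eight are taken at both visits) nor any planned conclusion. Setting medication changes beside the weight result, or adding confidence intervals, would be a reviewer's addition; the protocol plans no analysis of medication data.

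**Conclusion.** The three observations are accurate, and no change to the plan follows. The Medications and Medical history rows are most likely one clerical slip, a mark one row too high, and Height is another. Checking the original table and aligning these rows with the text is copy-editing. The double labelling concerns six questionnaires, and 4 against 9 (or 10 with weight) pre-post secondary measures, in a pilot with no confirmatory test. The silence on weight and waist is missing detail that an analyst would fill with the paired t-test or signed-rank test.

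This rests on three assumptions: that the written promise of a medication update governs over the empty cell, that the site chart is as complete as the protocol says, and that the pre-post results are reported as descriptive support for the focus-group findings. The last is how the protocol frames them, since Section 4a calls the comparison secondary. If a later trial in this programme used weight change or these questionnaires to support an efficacy claim, a single outcome list and a stated method would matter there.

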We will conduct descriptive analyses of baseline data. Our acceptability outcomes among consumers will include their satisfaction with the intervention as well as program attendance. Our behavior change outcomes among consumers will include changes in dietary and physical activity measures pre-post. We will examine changes in diet and physical activity outcomes with t-tests and Chi Square tests, as appropriate. If these outcomes are not normally distributed, then we will use Wilcoxon signed-rank tests in lieu of t-tests.

c. Statistical plan including sample size justification and interim data analysis.
Not applicable to qualitative data collection

d. Early stopping rules.
Not applicable

8. Risks

a. Medical risks, listing all procedures, their major and minor risks and expected frequency.

ACHIEVE-D Intervention Risks.

The 2 month behavioral weight loss intervention sessions should be minimal risk for participants. Physical activity may pose a small risk of musculoskeletal injury. In addition, making dietary changes and engaging in moderate-intensity exercise may also pose risks such as needing to adjust the dose of certain medications (e.g., hypoglycemic agents) or may be inappropriate for people with certain medical conditions.

Focus Group Risks. This study involves focus group discussion. Every effort will be made to protect confidentiality. There is minimal risk to the participant. If a participant changes her/his mind and does not wish to complete the focus group discussion, s/he will be allowed to leave.

Data Collection Risks. Risks related to the data collection include loss of confidentiality, and potential discomfort, boredom or inconvenience from participating in a focus group and answering survey questions and undergoing anthropometric measurements.

b. Steps taken to minimize the risks.

Minimizing ACHIEVE-D Intervention Risks.

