Participant safety will be closely monitored. Protection of research participants begins with the eligibility criteria, which are designed to exclude individuals with a serious medical condition that would preclude their ability to lose weight or to exercise safely. This will be done in collaboration with the participant's primary care physician. During the study, clinical care will be provided by the participants' usual specialty mental health providers and the primary care physician, not by the study. Participants will be made aware of this delineation of responsibility. We will carefully monitor the safety of enrolled participants. Participants will be educated about symptoms to look for (e.g., low blood sugar). If a participant develops a medical problem, the safety of continuing or resuming the intervention will be ascertained by the participant's primary care physician in collaboration with a study clinician.

Consumers will be screened for orthopedic or rheumatologic problems that might limit their ability to participate in the physical activity component of the intervention. Exercise classes will focus on mild to moderate intensity aerobic exercise using progression of intensity and duration appropriate for sedentary individuals. Staff will be trained to identify signs and symptoms of cardiovascular events in accordance with CPR training. In the case of illness or injuries during the intervention period (e.g., motor vehicle accident), interventionists continue to advise consumers on adapting

their physical activity program. If there is any question about the etiology of an injury or the need for treatment, the consumer will be referred to a physician for further evaluation.

Minimizing Focus Group Risks. We will minimize risk of group discussions by advising participants that by agreeing to be in this study, they are agreeing not to talk about any personal details that other individuals share in the focus group. Participants will be informed that they do not have to participate in any group discussion where they feel uncomfortable and can leave the session at any time.

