Minimizing Data Collection Risks. There is a risk of the loss of confidentiality of medical information. We will ensure protection of the data and any personal health information. Only the study team will have access to participant's identifying information. Each participant will be assigned an identification (ID) number at the time of recruitment. The database that links the ID with the participant will only be accessible by the principal investigator and core investigative team. Data will be stored in RedCap and when exported on a Hopkins (JHMCIS managed) network drive which is password-protected and backed-up each night. If a participant changes her/his mind and does not wish to complete the study s/he may withdraw at any point.

Participants will be aware through the consent process that videos will be taken of the group sessions and that clips may be incorporated into future training materials or posted on [name] research website.

There is a risk of potential stress, discomfort, boredom or inconvenience from answering survey questions and undergoing anthropometric measurements. Participants will be informed that they do not have to answer any questions that they do not wish or have their waist circumference, height, or weight measured. There are risks related to interview location at the PRP. To ensure participants' privacy, we will conduct interviews in a private space.

c. Plan for reporting unanticipated problems or study deviations.

Unanticipated problems or study deviations will be reported to the IRB, the NIH, and if applicable to all study participants in a letter.

d. Legal risks such as the risks that would be associated with breach of confidentiality.

None

e. Financial risks to the participants.

None

9. Benefits

Consumers may benefit from participating to increase their knowledge about healthy diet and physical activity. This study may provide benefit to society at-large, as our results will help us determine whether the ACHIEVE-D curriculum is acceptable to consumers with SMI. We believe that the risks to subjects are minimal and reasonable given the knowledge to be gained. There are no direct benefits to the PRP staff or peer leaders; however, their input is likely to improve the design and implementation of the ACHIEVE-D curriculum in a future trial.

Date: May 15, 2019

Principal Investigator: [name]

Application Number: IRB00194122

10. Payment and Remuneration

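### Does the plan need a scheduled harms record, given that it names injury and medication-dose changes as risks and Table 3 disagrees with the text on medications?

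*Combined protocol and SAP*

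**What the plan says.** Section 8a, under a form heading that reads "Medical risks, listing all procedures, their major and minor risks and expected frequency", gives two specific risks. The first is "Physical activity may pose a small risk of musculoskeletal injury". The second is that dietary change and moderate exercise "may also pose risks such as needing to adjust the dose of certain medications", with glucose-lowering drugs as the example. It adds that such changes may not suit people with certain conditions.

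Section 8b states: "We will carefully monitor the safety of enrolled participants". It then describes what happens if a medical problem, illness or injury arises. Section 8c gives a reporting route: "Unanticipated problems or study deviations will be reported to the IRB", and also to the NIH.

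On collection, section 4 says of the intervention period that "we will also collect data on participants regarding attendance, weight from weigh-ins during the sessions", followed by exercise hours and weekly diet and activity logs. Its Medications paragraph ends: "Medication information will be updated at the end of the pilot intervention". Its Medical History paragraph places that item at screening. In "Table 3. Data Collection Schedule", Medications has a single cross, under Consent/Screening, and Medical history has crosses under Consent/Screening and Post.

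**The concern.** A protocol that names harms and promises to watch for them would normally show where they are written down. Here the schedule has no such place. The two rows that might serve, Medications and Medical history, both appear to disagree with the text, and in opposite directions.

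The pilot is meant to shape materials and procedures for a later trial. If nobody is asked about harms in a standard way, its report could not separate an absence of harm from an absence of recording. Section 8c does not obviously help, because it covers unanticipated problems and the two named risks are anticipated.

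**Working it through.** **Count of Table 3.** There are 23 data rows. Crosses by column:

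| Column | Rows marked |
|---|---|
| Consent/Screening | 8 |
| Baseline | 10 |
| During | 4 (weight; attendance and exercise; food and activity logs; coach fidelity) |
| Post | 15 |

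Rows for adverse events, injuries or symptoms: 0. Section 7 contains no safety summary. This part of the concern is right.

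**Text against table for the two rows.**

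| Item | Section 4 text | Table 3 |
|---|---|---|
| Medications | baseline list, then update at the end | screening only |
| Medical history | screening | screening and Post |

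*Medications.* This is a plain disagreement, but it does not mean that dose changes go unrecorded. The same paragraph says the site keeps track of every medicine and every change to it. The study's first list is compiled from that chart, and participants consent to review of their records at the site. The text explicitly plans the end update. What is missing is a Post cross.

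*Medical history.* The text says when the item is collected but does not say that it is collected only then. The paragraph before Table 3 says other measures are repeated as the table sets out. A Post repeat is therefore compatible with the text, and this is not a firm contradiction.

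*Common cause.* The two rows are adjacent. Moving the single Post cross down one line would resolve both mismatches, so a slip in the source or in reading the table is a plausible explanation.

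**Provision for harms outside the table.** Section 8b has illness or injury lead to advice on adapting activity, sends doubtful or treatable injuries to a physician, and has the primary care physician and a study clinician judge whether continuing is safe. Classes meet three times a week with an interventionist, so staff are in regular contact with attenders. Section 5 excludes medication-dependent diabetes, which largely removes the example given for the medication risk.

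**What a scheduled count would yield.** If *n* consumers are all asked and none reports an event, the one-sided 95% upper bound on the event risk is 1 − 0.05^(1/n).

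- n = 10 (the planned enrolment): 1 − 0.05^(1/10) = 0.259
- n = 8: 0.312
- n = 12: 0.221

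The range 8 to 12 is an assumption around the stated figure of about 10. Even complete ascertainment with no events would leave a risk of roughly one in four open.

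**What it would cost.** Asking at each weekly weigh-in and at the Post visit means 10 × 8 + 10 = 90 entries, if everyone attends throughout. Weigh-ins take place at sessions, so this figure excludes the work of tracing consumers who stop coming, who are the ones most likely to have been hurt.

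**The case for a change.** The strongest case for acting is that every provision in section 8 begins once a problem is known, and none says how problems are found or counted. The focus group asks about difficulties, but it is one session at the end, and a consumer who left because of an injury may not be there. Session videos are graded for fidelity and cannot show exercise done elsewhere, which participants are encouraged to do. The protocol administers its instruments by interview because of low literacy and cognitive problems, and the same reasoning favours a prompted question over spontaneous report. One row and one sentence would be cheap.

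Much of this stands as description. No prospective injury item is scheduled, the condition checklist is not said to cover injuries, and the pilot's report will not be able to give a harms rate. The expected frequency that the form's heading asks for is also absent, though that is a matter of completing the form.

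What does not stand is the step from there to a defect in the plan. The record of medication changes exists at the site. The documents mention no injury log, but staff who must monitor, refer, decide on continuation and report would ordinarily keep one; that is an inference. The cheap version of the extra row misses the leavers who motivate it, and the version that reaches them has not been costed.

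**Conclusion.** No change to the plan follows. The concern combines a clerical mismatch (a Post cross absent from the Medications row, possibly displaced to the row above) with missing operational detail (no injury or adverse-event row among 23). Neither alters a result the pilot is designed to give. Its primary outcomes are acceptability and feasibility, judged from focus groups; it has no safety objective, and no stated rule would give a wrong answer. The text on the medication update is explicit enough for staff to follow whatever the table shows.

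The statistical gain from a formal count would be small: a zero from 10 people excludes only risks above about 26%. This conclusion assumes that enrolment is near 10, that the site's chart is kept as described, and that the monitoring promised in section 8b is carried out with ordinary record-keeping. It would not carry over to a larger trial or to one with a safety aim.
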